**Post Treatment Follow-up Visits**

**Post Treatment Week 4 (SVR4) - Week 10 (Shortened treatment) or Week 16 (Standard treatment) (+/- 3 days)**

- LFTs, FBC and biochemistry
- Pregnancy test (females of child bearing potential only)
- Adverse Events
- Research specimen collection (EDTA plasma & ACD Plasma/PBMCs \*)

\*To be collected in patients with suspected relapse/reinfection only

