### 11.3 Analyses

Efficacy analyses:

There will be one primary pair-wise comparison of the efficacy endpoints: shortened duration therapy versus standard duration therapy. Comparisons will be simple, direct two-sample comparisons of randomised treatment groups unadjusted for baseline covariates. If there is evidence of substantial imbalance at baseline in important covariates, further adjusted analyses will also be performed. If any randomisation mistakes occur, such that patients incorrectly receive the wrong treatment, then key efficacy endpoints will be performed where these patients will be excluded.

The primary analysis will compare randomised treatment groups on an ITT basis including all available data. The primary endpoint, SVR12, will be calculated for each patient based on all available data. Treatment arms will be regarded as non-inferior if the difference in proportion between regimens has a lower limit greater than -12%. Secondary analyses will compare randomised treatment groups based on available data (per protocol).

Proportions and 95% confidence intervals will be reported for both the primary and secondary virological endpoints. These will be provided overall, by treatment duration, by HCV genotype and by HIV status, and will be assessed for both the ITT and PP populations.

SVR 4, SVR 12 and SVR 24 rates will be compared to SVR rates demonstrated in historical controls in the ATAHc I, ATAHc II, DARE-C I and DARE-C II studies. Differences in proportions between studies will be summarised as n (%) in each group, with percent difference between cohorts with 95% confidence interval.

Factors associated with ITT study population treatment efficacy will be evaluated by univariate analysis, and will include, but are not limited to, the following variables: socio-demographic factors (age, gender, ethnicity); virological factors (baseline HCV viral load, HCV genotype); risk behaviors (injecting drug use, sexual behaviour); and HIV co-infection.

Additional treatment efficacy evaluations will be conducted among the *per protocol study population*, defined as subjects who receive >80% of planned treatment.

The impact of 80/80 adherence, 90/90 adherence, 100/100 adherence, on-treatment adherence and early discontinuation on SVR will also be evaluated.

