- To evaluate the immunological factors associated with treatment induced clearance and reinfection;
- To evaluate patient interest and attitudes towards long acting parenteral hepatitis C therapy (Long-Acting Hepatitis C Therapy Questionnaire).

Hypothesis

Six weeks treatment with sofosbuvir/velpatasvir is non-inferior to twelve weeks treatment with sofosbuvir/velpastavir as assessed by sustained virological response at 12 weeks post treatment in the intention-to-treat population (SVR12).

Study design (Figure 1)

This is an open label multicentre study. The study consists of a screening phase, treatment phase and follow-up phase to evaluate treatment response and reinfection. Participants will be required to wait a minimum of four weeks from screening before commencing treatment to assess for spontaneous clearance. The maximum wait period allowed between screening and baseline is 12 weeks.

[figure not shown]

Figure 1: Study Schema

Sample size and power

The primary objective of this trial is to establish the non-inferiority of short duration treatment (6 weeks) to the standard duration treatment (12 weeks). Assuming an expected SVR of 90% in the control arm, 113 participants per arm will be required to give 80% chance that the two-sided confidence interval of the difference between regimens has a lower limit greater than -12%.

A total of 250 subjects enrolled and randomised will comprise the intention-to-treat (ITT) population and will form the study population for evaluation of the primary and secondary endpoints.

TYPE OF ANALYSIS

This document describes the primary statistical analysis for REACT study in accordance with protocol version 5.0.

Data Safety and Monitoring Board (DSMB) Analysis

This study has a DSMB to review the progress and safety of the study. The DSMB conducted an interim safety and adherence analysis when the first 50 participants had either reached post-treatment week 12 or dropped out of the study and then when a further 10 per arm reached 12 weeks post treatment. At the second review the DSMB recommended termination of the short arm of the study due to inferiority. At the stage of the DSMB recommendation, a total of 196 participants had been randomised, 192 had completed their randomised treatment, a further 4 were randomised to receive 6 weeks and extended to 12 weeks. Therefore, the primary analysis population will be based on 192 participants (99 in standard Arm, and 93 in shortened arm).

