The modified Intention to Treat (mITT) population includes participants in the FAS excluding those with non-virological reasons for treatment failure (i.e., death, loss to follow up) and reinfection. Participants with confirmed reinfection after achieving an ETR, but prior to the primary efficacy endpoint (SVR12), will be excluded from the mITT.

Per-protocol Analysis Set

The PP population is defined as all participants who received >90% of scheduled treatment for >90% of the scheduled treatment period with follow-up virologic data to SVR12.

Safety Population

The Safety population includes all participants who randomised and will be analysed and presented according to the actual on-treatment monitoring arm received during the study.

The ITT population will be used for primary efficacy analyses, and the safety population will be used for all safety analyses.

Data Handling Conventions

Missing Data

For the analyses of categorical HCV RNA data, missing post-treatment HCV RNA data will have the missing data imputed. Missing on-treatment HCV RNA will have the missing data imputed up to the time of the last dose.

If a data point is missing and is preceded and followed in time by values that are "<LLOQ, TND," then the missing data point will be set to "<LLOQ, TND."

If a data point is missing, and preceded and followed by values that are "<LLOQ, target detected," or preceded by "<LLOQ, target detected" and followed by "<LLOQ, TND," or preceded by "<LLOQ, TND" and followed by "<LLOQ, target detected," then the missing value will be set to "<LLOQ, target detected."

If a data point is missing, and preceded and followed by values that are ">LLOQ, target detected," or preceded by ">LLOQ, detected" and followed by "<LLOQ, target detected" or "<LLOQ, TND", then the missing value will be set to ">LLOQ, target detected."

The following scenarios describe a framework for analysis of the primary endpoint based on various anticipated events for the ITT and mITT population:

- i. In the event of the participant dying or becoming lost to follow-up prior to SVR 12, the participant will be considered to have failed treatment (loss to follow up = failure)
- ii. If the SVR 12 time-point measure is missing, then the next available measure (i.e., SVR 24 or later) will be used. If no future time points are available, the participant will be considered a treatment failure.

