	To evaluate patient interest and attitudes towards long acting parenteral hepatitis C therapy (Long-Acting Hepatitis C Therapy Questionnaire)	Not included in primary analysis	

Primary efficacy endpoint

The proportion of participants with HCV RNA below the level of quantitation (target not detected [TND] or target detected, not quantifiable [TDnq]) at 12 weeks post end of treatment (SVR12)

The primary analysis will compare randomised treatment groups on an ITT basis including all available data. The primary endpoint, SVR12, will be calculated for each patient based on all available data. Treatment arms will be regarded as non-inferior if the difference in proportion between regimens has a lower limit greater than -12%. Secondary analyses will compare randomised treatment groups based on available data (per protocol).

Secondary efficacy endpoints

- Virological endpoints
 - The proportion of treated participants with:
 - ETR (defined as undetectable plasma HCV RNA at the end of treatment)
 - SVR4 (defined as undetectable plasma HCV RNA at post-treatment week 4)

For virological endpoints, the point estimates and 95% exact confidence intervals will be reported by study arm, by HCV genotype and by HIV serostatus.

Virological endpoints (Table 13 and 14)

The presence of HCV RNA will be assessed at all scheduled clinic study visits using Aptima HCV Quant Dx assay, version 2.15.5 (lower limit of quantitation [LLOQ] 10IU/mL; Hologic, Inc., Marlborough, MA, USA), with centralised testing performed at St Vincent's Centre for Applied Medical Research (Sydney, NSW, Australia).

Proportions and 95% confidence intervals will be reported for both the primary and secondary virological endpoints. Virological endpoints will be assessed in the ITT, mITT and PP populations, with results stratified by HCV genotype/subtype and HIV serostatus.

Factors associated with treatment outcome in the ITT population will be evaluated by univariate analysis. Variables assessed will include but are not limited to: demographic factors (age, gender); virological factors (baseline HCV RNA, genotype 1 subtype, duration of HCV infection); risk behaviors (injecting drug use, sexual behavior, mode of HCV acquisition); HIV co-infection; treatment factors (adherence).

Primary safety endpoints

The primary safety endpoints are:

- Proportion of participants with common adverse events (reported by greater than 5% of the study population);

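### The SAP per-protocol set removes a participant with documented relapse and no later sample, instead of counting a known failure

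*SAP*

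**What the plan says.** The SAP (Per-protocol Analysis Set) defines PP as "all participants who received >90% of scheduled treatment for >90% of the scheduled treatment period with follow-up virologic data to SVR12". The condition on virologic data is new in the SAP. Protocol 11.3 has a PP population "defined as subjects who receive >80% of planned treatment", with no such condition. The different adherence cut-offs are a separate matter.

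Under Missing Data, the SAP gives two rules for the primary endpoint: death or loss to follow-up before SVR12 is failure, and "If the SVR 12 time-point measure is missing, then the next available measure (i.e., SVR 24 or later) will be used", with failure if nothing later exists. These are introduced as a framework "based on various anticipated events for the ITT and mITT population". PP is not named. The same section has a general imputation rule for HCV RNA that is not tied to one analysis set, but it needs a value before the gap and a value after it.

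The SAP's Study Definitions treat recurrent viraemia up to SVR12 as relapse unless reinfection is confirmed. SAP Table 2 puts HCV RNA from post-treatment days 21 to 69 in the week 4 window and from days 70 to 146 in the week 12 window. Table 12 lists a non-inferiority comparison in the PP population as a secondary endpoint.

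**The concern.** Relapse is the expected way for a shortened course to fail, and it can be on record before any SVR12 sample is due. Such a participant has a known outcome. A rule that needs data to SVR12 removes this participant because a later sample is absent, while a participant who was suppressed at week 4 and attended SVR12 stays in as a success. Membership then depends partly on outcome.

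The case can arise in practice. The protocol's SVR4 visit has no local HCV RNA test. Its virology rests on the stored item "Research specimen collection (EDTA plasma & ACD Plasma/PBMCs" (the PBMC part only if relapse or reinfection is suspected). Protocol 10.1 and 10.2 have samples kept at site for bulk shipment, on instruction. A week 4 relapse may therefore come to light only after the participant has been lost.

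In a non-inferiority trial the PP result is read as a check on the ITT result. If known failures leave mainly the short arm, that check leans towards non-inferiority.

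**Working it through.** **1. Head count.** From the SAP (DSMB Analysis): 99 + 93 = 192 in the primary analysis population, and 192 + 4 extended participants = 196 randomised. The figures agree.

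**2. What happens to a relapse with no later sample.** Take a participant with more than 90% of treatment, quantifiable HCV RNA at post-treatment day 28, and no further sample.

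- ITT: loss to follow-up before SVR12, or a missing SVR12 with nothing later, is failure.
- General imputation: not available, because there is no later value.
- PP: no data to SVR12, so removed. No rule counts the participant as a failure.

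If a later sample exists, the imputation rule sets the gap to above LLOQ. The SAP does not say whether an imputed value satisfies the PP data condition.

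**3. Effect of one dropped failure.** With x successes among n, dropping one failure raises the rate by x/(n−1) − x/n = x/[n(n−1)]. The documents give no outcome data, so these counts are assumed.

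- Short arm 77/88: 77/(88 × 87) = 1.0 point.
- Short arm 78/93: 78/(93 × 92) = 0.9 point.
- Standard arm 86/92: 86/(92 × 91) = 1.0 point, in the opposite direction for the difference.

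**4. Interval against the −12 point margin, first set of assumed counts.** Newcombe 95% interval, with lower limit d − √[(p₁ − l₁)² + (u₂ − p₂)²], where l and u are Wilson limits and arm 1 is the 6-week arm. For 77/88 v 86/92: d = 87.50 − 93.48 = −5.98; l₁ = 78.99; u₂ = 96.98; lower limit = −5.98 − √(8.51² + 3.50²) = −15.2.

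| Failures dropped (short, standard) | Short | Standard | Difference (95% CI), points |
|---|---|---|---|
| 0, 0 | 77/88 | 86/92 | −6.0 (−15.2, 2.8) |
| 1, 0 | 77/87 | 86/92 | −5.0 (−14.1, 3.7) |
| 2, 0 | 77/86 | 86/92 | −3.9 (−12.9, 4.6) |
| 3, 0 | 77/85 | 86/92 | −2.9 (−11.7, 5.5) |
| 3, 1 | 77/85 | 86/91 | −3.9 (−12.6, 4.2) |
| 2, 2 | 77/86 | 86/90 | −6.0 (−14.7, 2.0) |

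Among these cases the margin is crossed only when three failures leave the short arm and none leaves the standard arm.

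**5. Second set of assumed counts.** Standard arm 89/99; lower limit d − 1.96 × SE, with SE² = p₁(1−p₁)/n₁ + p₂(1−p₂)/n₂.

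| Short arm, all kept | Difference (lower limit) | Four short-arm failures dropped |
|---|---|---|
| 73/93 | −11.4 (−21.7) | 73/89: −7.9 (−17.8) |
| 78/93 | −6.0 (−15.6) | 78/89: −2.3 (−11.3) |
| 84/93 | +0.4 (−8.0) | 84/89: +4.5 (−3.1) |

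Only the middle row changes its conclusion. Dropping two from each arm moves the difference by 0.15 point or less in every row. Dropping two from the standard arm alone moves it down by about 1.9 points.

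**6. The four extended participants.** If they were added to 77/88 in the short arm, all with SVR12, the result is 81/92 v 86/92: −5.4 (−14.3, 3.2). With three of four, 80/92 gives −6.5 with a lower limit of −15.6, which is further from non-inferiority. If PP is drawn from the 192, the effect is zero.

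**The case against.** The strongest reply is that the case is rare. Protocol section 7 has re-viraemic participants seen monthly for six months with HCV RNA each time, the week 12 window runs to day 146, and a later sample may allow imputation. This stands as a limit on frequency, not as a cure: the monthly visits begin only once re-viraemia is known, and imputation needs a later value.

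The illustration is also fragile. Two dropped instead of three, or three against one, leaves the margin uncrossed, and no document supports any particular count or split. That stands in full.

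The loss would be visible. The SAP summarises exclusions from each set with reasons, tabulates relapse by arm (Table 17) and lists virological failures individually. These displays let a reader see the problem, but they do not correct the PP estimate.

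Finally, PP is secondary, the hypothesis is framed in the ITT population, and the DSMB had already recommended ending the short arm for inferiority. This limits the consequence.

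A reader might go further and infer a second bias: PP has no upper limit on exposure, and the SAP reports that "a further 4 were randomised to receive 6 weeks and extended to 12 weeks". The documents do not support this. The SAP's next sentence bases the primary analysis on 192 participants without those four, and Table 3 lists ITT, mITT and PP together as analysis populations. The four could re-enter only because the FAS is also defined as all randomised and the PP text, unlike the mITT text, names no parent set. That is an ambiguity. Nor does protocol 11.3 settle it. Its rule for leaving such participants out opens with "If any randomisation mistakes occur, such that patients incorrectly receive the wrong treatment, then key efficacy endpoints will be performed where these patients will be", so it covers randomisation mistakes, not an extension of treatment.

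**Conclusion.** The gap is real on the text. A participant with documented relapse and no later sample is removed from PP when the outcome is known to be failure. The size is about 1 percentage point in the difference for each short-arm participant dropped, on assumed counts. The direction depends on where the relapses fall: towards non-inferiority if they are mainly in the 6-week arm, which the DSMB recommendation makes plausible; the reverse if they are mainly in the standard arm; and close to nil if they are similar in both. The number of cases is not known from the documents and is probably small. The primary ITT analysis is not affected.

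Two stronger inferences are not supported. It is not shown that the PP conclusion would change; that needs one-sided counts chosen for illustration. It is not shown that the four extended participants bias PP; even if all four were added as successes, the assumed result would still miss the margin.

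**What to change.** Redefine PP as members of the 192-participant primary analysis population who received more than 90% of assigned treatment and have a known SVR12 outcome. A known outcome is any of:

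- an HCV RNA result in the post-treatment week 12 window;
- if that is missing, the next available later result, as ITT and mITT already allow;
- documented virological failure before it (non-response, breakthrough, or quantifiable post-treatment HCV RNA not confirmed as reinfection), counted as failure in both arms.

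The second item keeps the rule even-handed. Without it, early failures would be retained while a participant who missed the week 12 window and was suppressed at SVR24 would be dropped. The failure types should be spelled out, because the SAP's Study Definitions describe virologic failure as non-response only, whereas Table 13 adds breakthrough and relapse.

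As a clarification only, state that the four participants extended from 6 to 12 weeks are not in the short-arm PP set.

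The cost is a paragraph of SAP wording and one derivation. The PP rate may come out slightly less favourable.

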Primary analysis: Post-treatment week 12

The analysis for the primary endpoint, SVR12, will be conducted after all participants have completed the post-treatment week 12 visit or prematurely discontinued from study. All the safety and efficacy data through to the post-treatment week 12 visit will be cleaned, finalised, and included for the analysis.

GENERAL CONSIDERATIONS FOR DATA ANALYSES

Statistical Methods

Analysis results will be presented using descriptive statistics. For categorical variables, the number (n) and percentage of participants in each category will be presented. For continuous variables, the number of participants (n), mean and standard deviation (SD), median, interquartile range (IQR, Q1-Q3), range (minimum, maximum) will be reported; for inclusion in the manuscript, an appropriate determination will be made depending on the variable, size and distribution of the population studied.

Statistical tests will be 2-sided and performed at the 5% significance level unless specified.

For all efficacy endpoints, means and proportions with two-sided 95% confidence intervals (CI) will be determined. For the analysis of categorical outcomes, Chi-squared tests or exact equivalents (for small numbers) will be used. For comparison of continuous measures, t tests or non-parametric equivalents will be used as appropriate for the observed data distribution. Changes in injecting behaviour between screening, end of treatment and post-treatment week 12 will be compared using the McNemar test (exact binomial probability).

Analysis Sets

Analysis sets define the subjects to be included in an analysis. The number of participants eligible for each analysis set will be provided. Participants who were excluded from each analysis set will be summarised, with reasons for exclusion.

Full Analysis Set (ITT population)

The FAS includes all enrolled participants who were randomised. This will be the analysis set used for the primary efficacy and safety endpoints. Following the DSMB recommendation to cease the study, the primary analysis population will be based on 192 participants (99 in standard Arm, and 93 in shortened arm).

Modified Full Analysis Set

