Where appropriate, safety data for subjects who did not complete the study will be included in summary statistics.

For example:

- If a participant took at least 1 dose of study drug, the subject will be included in a summary of adverse events according to the treatment received; otherwise, if the subject is not dosed, then they will be excluded from the summary.
- If safety laboratory results for a participant are missing for any reason at a time point, the subject will be excluded from the calculation of the summary statistics for that time point.

Values for missing safety laboratory data will not be imputed; however, a missing baseline (day 0) result will be replaced with a screening result, if available.

Outliers

Outliers will be identified during data management and data analysis process, but no sensitivity analyses will be conducted. All data will be included in the data analysis.

Data Handling Conventions and Transformations

HCV RNA values below the LLOQ for the assay will be set to the lower limit minus 1 for the calculation of summary statistics for the actual HCV RNA values and the change from baseline values by study visit.

For selected analyses, HCV RNA data (IU/mL) will be transformed to the logarithmic (base 10) scale (\log_{10} IU/mL).

Visit Windows

Definition of Study Day

Study day will be calculated from the date of first dose of study drug administration and derived as follows:

- For post-dose study days: Assessment Date minus First Dose Date + 1
- For days prior to the first dose: Assessment Date minus First Dose Date

The last dose date for an individual study drug will be the end date entered in the Treatment Termination or Drug Administration eCRF.

The last dose date of treatment for a given participant will be defined as the maximum of the last dose dates of individual study drugs in a treatment group, if applicable.

If there are participants for whom the date of last study drug is unknown (lost to follow-up and not able to be contacted), the date of last dose will be estimated using the maximum of non-missing study drug start or stop dates, visit dates, and laboratory collection dates (post-treatment visits and unscheduled visits are not included).

Analysis Windows

Participant visits might not occur on protocol-specified days. Therefore, for the purposes of analysis, observations will be assigned to analysis windows (**Table 1** and **Table 2**).

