All participants who receive at least one dose of study drug will be included in the safety analyses. Safety analyses will be performed overall and by treatment arm. Safety will be evaluated by assessment of clinical laboratory tests at various time points during the study, and by the documentation of AEs.

All safety data collected on or after the first dose of study drug administration up to 30 days after the last dose of study drug will be summarised.

Extent of Exposure

A participant's extent of exposure to study drug will be generated from the study drug administration page of the eCRF.

Adverse Events

Clinical and laboratory AEs will be coded using the Medical Dictionary for Regulatory Activities (MedDRA, [insert version](#)). System organ class (SOC), high level group term (HLGT), high level term (HLT), preferred term (PT), and lower level term (LLT) will be provided.

Events will be summarised on the basis of the date of onset for the event.

A treatment-emergent AE (TEAE) will be defined as:

- Any AEs with an onset date on or after the study drug start date and no later than 30 days after permanent discontinuation of study drug
- Any AEs leading to premature discontinuation of study drug

Adverse Event Severity

Adverse events are graded by the investigator as mild (Grade 1), moderate (Grade 2), severe (Grade 3), or life-threatening (Grade 4) according to toxicity criteria specified in the protocol. The severity grade of events for which the investigator did not record severity will be categorized as "missing" for tabular summaries and data listings, and the most severe will be considered (for sorting purpose only) in data presented. For example, if an adverse event of the same type (PT) is listed more than once for an individual, the highest grade will be used to summarise severity.

Relationship of Adverse Events to Study Drug

Related AEs are those for which the investigator selected "Related" ("Possibly related" or "Probably related") on the AE CRF to the question of "Related to Study Treatment." Events for which the investigator did not record the relationship to study drug will be considered to be related to study drug for summary purposes.

Summaries of Adverse Events and Deaths

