The number and percentage of participants overall and in each arm with treatment-emergent adverse events will be tabulated by primary MedDRA System Organ Class (SOC) and preferred term (PT). The tabulation of the number of participants with treatment-emergent adverse events by severity grade and relationship to study drug also will be provided.

Participants reporting more than one adverse event for a given MedDRA PT will be counted only once for that term using the most severe grade for the severity grade table and the most related for

the relationship to study drug tables. Participants reporting more than one type of event within a SOC will be counted only once for that SOC, but both PTs will be listed.

Summaries of treatment-emergent AEs (by SOC and PT) will be provided for the following:

- All TEAEs
- TEAEs of Grade 3 or above
- All treatment-related TEAEs
- Treatment-related TEAEs of Grade 3 or above
- All SAEs (including death)
- All treatment-related SAEs
- All TEAEs leading to premature discontinuation of the study drug
- TEAEs that occurred in at least 5% of subjects within any treatment group

Adverse event summaries will provide the number and percentage of subjects with treatment-emergent AEs by SOC and PT, divided by treatment group.

Adverse events will be summarised and listed first in alphabetic order of SOC and then by PT in order of descending incidence of the pooled treatment groups within each SOC.

In summaries by severity grade, the most severe grade will be used for those AEs that occurred more than once in a participant during the study.

Serious adverse events (SAE)

The proportion of participants with at least one SAE will be reported overall. Serious adverse events will be summarized and relationship between the SAE and study drug will be detailed

Laboratory Evaluation

Selected laboratory data will be summarised (n, mean, SD, median, IQR, range) by study visit along with the corresponding change from Baseline/Day 1 to Post Treatment Week 12.

Depending on sample distribution, parametric or non-parametric tests can be used to compare the change in biochemical and haematological indicators over time.

The NIH DAIDS AE Grading Table Version 2.0- November 2014 will be used to grade severity.

Table 22. Safety parameters – adverse events and treatment discontinuation

Adverse events	Safety analysis set (N=XX)
Participants reporting any AE up to 30 days after last dose, n (%) Grades 1-2, n (%) Grade 3, n (%) Grade 4, n (%)	

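### The SAP defines the safety set two ways, and the randomised-only rule drops anyone who was dosed but never randomised

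*SAP*

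**What the plan says.** Two places in the SAP point to a randomised set. Under Safety Population, "The Safety population includes all participants who randomised", and the closing sentence of that part adds that "the safety population will be used for all safety analyses". Under Full Analysis Set, which is also restricted to randomised participants, the SAP says "This will be the analysis set used for the primary efficacy and safety endpoints". Protocol section 11.1 leans the same way: it makes the randomised ITT set the population for the secondary endpoints, and section 11.2 lists toxicity among these.

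Two other places point to a dosed set. The Safety Analyses section says "All participants who receive at least one dose of study drug will be included in the safety analyses". The missing-data conventions, in an example about participants who did not complete the study, say "If a participant took at least 1 dose of study drug, the subject will be included in a summary of adverse events". The treatment-emergent definition fits this rule, since it counts "Any AEs with an onset date on or after the study drug start date".

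On layout, "Safety analyses will be performed overall and by treatment arm". Table 22 has a single column for an undefined safety analysis set, Table 23 lists SAEs under Standard and Shortened only, and Table 24 has an all-participants column plus two arms.

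Protocol sections 4.1 and 4.2 start treatment at baseline and randomise between weeks 5 and 6. Protocol section 11.2 also calls for toxicity to be evaluated in those who withdraw before randomisation.

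**The concern.** Both rules claim every safety analysis, and they cannot both hold if anyone was dosed and not randomised. Because randomisation comes five to six weeks after the first dose, the randomised-only rule makes entry to the safety set depend on having stayed in the study that long. Anyone who stopped earlier, for toxicity or any other reason, is left out of the headline rates of adverse events, SAEs, discontinuations and deaths.

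Tolerability would look better than it was if the omitted people had a higher event rate than those randomised, and slightly worse if theirs was lower. The choice should not be left to whoever programs the tables.

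**Working it through.** **1. The SAP's own counts.** From the DSMB Analysis paragraph: 99 standard + 93 shortened = 192, and 192 + 4 randomised to 6 weeks but extended to 12 = 196 randomised. The counts agree. The point does not depend on the sample-size calculation.

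**2. The rules compared as sets.** Let R be the randomised participants and D those with at least one dose. Drug starts at week 0 and randomisation follows at week 5 to 6, so by design R lies inside D. The reverse group, randomised but never dosed, should be empty. With k the number dosed but never randomised, R = 196 and D = 196 + k. The rules agree only if k = 0.

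**3. Could k be above zero?** The protocol foresees such a group, since section 11.2 plans an evaluation of people who withdraw before randomisation. A second route is possible, by inference only. When the DSMB recommended ending the short arm, anyone in the first weeks of treatment might have remained unrandomised without withdrawing, and section 11.2 would not cover them. The documents do not say whether anyone was in either position.

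**4. Share of dosed participants left out by the randomised-only rule.** Formula: k / (196 + k), with k assumed.

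| k (assumed) | Dosed | Left out |
|---|---|---|
| 0 | 196 | 0% |
| 1 | 197 | 1/197 = 0.51% |
| 5 | 201 | 5/201 = 2.49% |
| 10 | 206 | 10/206 = 4.85% |

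**5. Effect on a reported rate.** Take a events among the 196 randomised and e among the k others. For k above zero:

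one-dose rate − randomised-only rate = (a + e)/(196 + k) − a/196 = [k/(196 + k)] × (e/k − a/196)

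The difference is positive only if e/k exceeds a/196. It is zero if the two rates are equal, and there is no difference at all if k = 0.

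Illustration with assumed values k = 5 and a = 2 discontinuations for adverse events:
- Randomised-only: 2/196 = 1.020%.
- One-dose, e = 0: 2/201 = 0.995%, a difference of −0.025 points.
- One-dose, e = 1: 3/201 = 1.493%, a difference of +0.472 points.

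**6. Do the table shells settle it?** No. Table 22 does not define its denominator. Table 24 could hold extra people in its all-participants column. Table 23 has no row for an SAE in someone without an arm, even under the one-dose rule. No SAP table covers the pre-randomisation withdrawals named in protocol section 11.2.

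**The case against.** The strongest reply is that this is one sentence against another, with no demonstrated consequence. The missing-data text is an example for non-completers and not a population definition. The treatment-emergent definition is an event window that applies equally to randomised participants. The protocol already requires toxicity in pre-randomisation withdrawals to be evaluated, so their events are not lost to the study. The SAP also promises the size of each analysis set, the reasons for exclusion, and a flowchart of those screened, enrolled and treated, so a gap between treated and analysed would be visible. The number affected may be nil. Finally, another fix would be consistent: keep the randomised set for the arm tables, amend the Safety Analyses sentence, and add the withdrawal summary.

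Much of this is fair. The missing-data example is weaker support, and the impact is unquantified. The conflict does not need that example, however: the Safety Population and Safety Analyses statements contradict each other directly. Listing exclusions makes a gap visible but does not say which denominator is right. The alternative fix would be consistent too, but the overall safety rates would still depend on reaching randomisation. It is true that people without an arm cannot inform the comparison of 6 with 12 weeks, and the change proposed below allows for that.

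**Conclusion.** The concern holds. The SAP gives two incompatible inclusion rules for safety and does not rank them, and the Safety Population definition is wrong as written for a design that doses before it randomises. Following it would give headline safety rates selected on reaching week 5 to 6.

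The size rests on k, which the documents do not give. Over an assumed range of 0 to 10, between 0% and 4.9% of dosed participants would be left out. In the illustration the discontinuation rate moves by −0.03 or +0.47 points. The direction is unknown, and if k is zero the two rules select the same people. The SVR12 result does not depend on this. The contradiction itself rests on the text alone and needs no assumption.

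**What to change.** - Define the Safety population as all participants who received at least one dose, state its N, and say that this definition governs every safety endpoint. Align the Full Analysis Set sentence that assigns safety endpoints to the randomised set.
- Report safety overall for this set, and by treatment arm received for randomised participants. Give those dosed but not randomised their own group in Tables 22 to 24. State where the 4 participants extended from 6 to 12 weeks are shown.
- Correct the reference in the Safety Population paragraph to a monitoring arm, since the arms in this trial are treatment durations.
- Add a table for the evaluation of pre-randomisation withdrawals required by protocol section 11.2.
- If no one was dosed without being randomised, one sentence saying so closes the point.

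The cost is one definition, one aligned sentence, an extra group in three tables and one summary table. No new data are needed, because protocol section 8.1.1 already has adverse events recorded during treatment and for 4 weeks after the drug is stopped. The drawback is a few more rows or columns and safety rates that may look slightly less favourable.
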